SD	Standard Deviation
SHSC	Sunnybrook Health Sciences Centre
SUADR	Serious Unexpected Adverse Drug Reaction
TSAT	Transferrin Saturation
WHO	World Health Organization

PROTOCOL SUMMARY

PRINCIPAL INVESTIGATOR	[name]
PROTOCOL TITLE	Daily vs. every other day oral iron supplementation in patients with absolute iron deficiency anemia (DEODO): a multi-centered, pilot randomized controlled trial
PROTOCOL NUMBER	1534
PHASE	III
INVESTIGATIONAL PRODUCT AND PLANNED USE	To evaluate the effectiveness of oral ferrous sulfate (oral iron), 300mg oral tablets and vitamin C 500mg, once daily versus every other day to improve hemoglobin 12 weeks post-initiation
STUDY DESIGN	A phase III, multi-centered, randomized, pragmatic, open-label, controlled pilot trial
DURATION OF FOLLOW-UP	From first dose of study drug to final study visit = 12 weeks
TREATMENT ALLOCATIONS	Experimental arm: Ferrous sulfate 300mg oral and vitamin C 500mg every other day x 12 weeks Control arm: Ferrous sulfate 300mg oral and vitamin C 500mg every day x 12 weeks
PATIENT POPULATION	Patients with iron deficiency anemia defined as hemoglobin less than 120 g/L in women or less than 130 g/L in men; AND ferritin less than 30 mcg/L
SETTING	A multi-centre study, outpatient clinical setting
PLANNED SAMPLE SIZE	52 patients The anticipated duration for this study's recruitment period is 2 years.

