3.4 Secondary Outcome Measures

Feasibility

1. Proportion of eligible patients consenting to participate
2. Proportion of consenting patients receiving the allocated treatment
3. Proportion of treated patients completing 4 week and 12 week laboratory tests
4. Proportion of treated patients completing 4 week, 8 week and 12 week FACIT-fatigue scale
5. Proportion of treated patients completing 4 week, 8 week and 12 week side effect questionnaire
6. Proportion of treatment doses taken as per protocol (adherence)
7. Proportion of treated patients taking at least 90% of their prescribed doses
8. Proportion of treated patients requiring a step down in therapy due to adverse side effects

Clinical/Safety

9. Mean hemoglobin increment at 4 and 12 weeks
10. Proportion with complete hemoglobin response defined as hemoglobin greater than or equal to 120 g/L at 4 weeks and 12 weeks for women and greater than or equal to 130 g/L at 4 weeks and 12 weeks for men.

11. Change in reticulocyte count at 4 and 12 weeks
12. Change in ferritin, serum iron, TSAT at 12 weeks
13. Quality of life (FACT-fatigue scale) at 4, 8 and 12 weeks
14. Proportion with side effects and type of side effects at 4, 8 and 12 weeks
15. Proportion of patients who stop taking oral iron due to side effects at 4 and 12 weeks
16. Need for escalation in therapy (need for alternative oral iron therapy (including if a participant in the every other day group escalates to daily iron), need for intravenous iron, need for transfusion, visit to emergency department related to anemia) at 12 weeks
17. Proportion of patients with a drop in hemoglobin of 10 g/L or more from baseline at weeks 4 and 12

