5.4.2 Follow-up Visits and Assessments

5.4.2.1 Week 1

Participants will be contacted by telephone or email for the following assessment at Day 7 ± 3 days

- Adherence as determined by patient diary (supporting documents)
- Side effect questionnaire (supporting documents)

5.4.2.2 Week 4

Participants will be contacted by telephone or email at Day 28 ± 7 days for the following assessment

- Adherence as determined by patient diary
- Side effect questionnaire
- FACIT-fatigue scale questionnaire
- Medication history (to confirm if any new or discontinued medications)
- Reminder to do laboratory tests (at the local site or local lab) for CBC, reticulocyte count

At the week 4 assessment, if the participant has a drop in hemoglobin of more than 10 g/L from baseline, then the patient will be referred back to the most responsible physician for management and escalation of therapy. If the patient receives escalation of therapy (need for alternative oral iron therapy including if a participant in the every other day group escalates to daily iron, need for intravenous iron, need for transfusion, visit to emergency department related to anemia), the participant will no longer complete any further study assessments and the most responsible physician will be notified. The reason for the drop in hemoglobin will be classified as: ongoing bleeding; non-compliance (defined as less than 50% of pills); other reason; or no clear reason.

5.4.2.3 Week 8

Participants will be contacted by telephone or email at Day 56 ± 7 days for the following assessment

- Adherence as determined by patient diary
- Side effect questionnaire
- FACIT-fatigue scale questionnaire
- Medication history (to confirm if any new or discontinued medications)

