5.4.2.4 Week 12 Final Study Visit

Participants will be assessed in person/remotely (telephone/zoom/OTN) at Day 84 ± 7 days for the following assessment

- Adherence as determined by patient diary and pill count
- Side effect questionnaire
- FACIT-fatigue scale questionnaire
- Medication history (to confirm if any new or discontinued medications)
- Laboratory tests: CBC, reticulocyte count, ferritin, serum iron and TSAT
- Need for escalation in therapy: Y/N
 - Increase in oral iron regimen from every other day to daily
 - Intravenous iron
 - Transfusion
 - Visit to emergency department related to anemia

5.4.2.5 Week 13

Participants will be contacted by telephone or email at $7 \text{ days} \pm 3$ days after the Week 12 final study visit for assessment of adverse and serious adverse events.

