16. Need for escalation in therapy (increase in oral iron regimen from every other day to daily, need for intravenous iron, need for transfusion, visit to emergency department related to anemia) assessed at 12 weeks
17. Proportion of patients with a drop in hemoglobin of 10 g/L or more at weeks 4 and 12

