10.0 CRITERIA FOR WITHDRAWAL AND DISCONTINUATION FROM STUDY

Patients will be followed until 12 weeks or until there is an escalation of therapy as defined by need for: alternative oral iron therapy (including if a participant in the every other day group escalates to daily iron), need for intravenous iron, need for transfusion, or a visit to emergency department related to anemia.

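### Section 7.2 item 16 and the week 12 checklist count only one oral escalation, every other day to daily, so oral changes in the daily arm go uncounted; the broader definition elsewhere reduces this and may remove it

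*Combined protocol and SAP*

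**What the plan says.** Item 16, need for escalation in therapy, is defined in two ways.

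- **Narrow.** Section 7.2 reads "Need for escalation in therapy (increase in oral iron regimen from every other day to daily, need for intravenous iron, need for transfusion", and adds an emergency visit related to anemia. The week 12 checklist in 5.4.2.4 has the same four entries, and its only oral one is "Increase in oral iron regimen from every other day to daily".
- **Broad.** Section 3.4 counts "need for alternative oral iron therapy (including if a participant in the every other day group escalates to daily iron", plus the same three non-oral events. The week 4 text in 5.4.2.2 has "need for alternative oral iron therapy including if a participant in the every other day group escalates to daily iron". Section 10.0 uses this meaning to end follow-up: "Patients will be followed until 12 weeks or until there is an escalation of therapy as defined by need for: alternative oral iron therapy".

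The Protocol Summary sets the comparator regimen: "Control arm: Ferrous sulfate 300mg oral and vitamin C 500mg every day x 12 weeks". Section 5.3.4 lets patients in either arm step down in frequency for side effects. After escalation at week 4, "the participant will no longer complete any further study assessments". Section 8.2 states an intention-to-treat analysis and a per-protocol analysis, but gives no estimator, test or handling rule for item 16. Appendix C schedules an escalation check at weeks 1, 4, 8 and 12 without saying which definition applies.

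**The concern.** An outcome compared across arms should give both arms the same chance of being counted for the same need. Under the narrow wording, an every-other-day patient who needs more oral iron and moves to daily dosing is an event. A daily-arm patient with the same need, met by another product or by more of the same product, is not. The counting rule could therefore make the experimental schedule look as if it fails more often when the underlying need is equal.

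The narrow wording also conflicts with the protocol's own rule for ending follow-up. Under 10.0, a daily-arm patient moved to an alternative oral iron has escalated and leaves follow-up. Under 7.2, the same patient has no escalation event.

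At stake are the by-arm escalation estimates that the pilot passes to the design of the definitive non-inferiority trial.

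**Working it through.** **Step 1. Plan's figure.** The documents give no rate, power or sample size for item 16, so there is nothing to reproduce. The only input they supply is 26 patients per arm (5.1).

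**Step 2. Routes that count, for patients on their assigned schedule.**

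| Event | 7.2 and 5.4.2.4: every other day | 7.2 and 5.4.2.4: daily | 3.4, 5.4.2.2, 10.0: every other day | 3.4, 5.4.2.2, 10.0: daily |
|---|---|---|---|---|
| Every other day to daily | yes | not possible | yes | not possible |
| Alternative oral iron | no | no | yes | yes |
| More of the same product, above daily | – | no | – | not stated |
| IV iron, transfusion, emergency visit | yes | yes | yes | yes |

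The narrow wording gives four routes against three, and none of the daily arm's three is oral. The broad wording gives both arms an oral route. Its remaining unevenness is that a frequency increase of the same tablet is named for one arm only.

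**Step 3. Size, under assumed rates.** Let s be the proportion in each arm with IV iron, transfusion or an emergency visit. Let q be the proportion of the remainder needing more oral iron, equal in both arms. Let f be the share of the daily arm's oral need that the definition counts. All of the every-other-day arm's oral need is taken to be met by moving to daily.

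- Every other day: pE = s + (1 − s)q
- Daily: pD = s + (1 − s)qf
- Gap produced by counting: (1 − s)q(1 − f)

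With s = 0.10 and q = 0.10, pE = 0.10 + 0.90 × 0.10 = 0.19. The last column treats the two arms' counts as independent binomials with n = 26.

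| f | pE | pD | Gap | Expected counts of 26 | P(more events in every-other-day arm) |
|---|---|---|---|---|---|
| 0 | 19.0% | 10.0% | 9.0 points | 4.9 vs 2.6 | 0.77 |
| 0.5 | 19.0% | 14.5% | 4.5 points | 4.9 vs 3.8 | 0.60 |
| 1 | 19.0% | 19.0% | 0 | 4.9 vs 4.9 | 0.43 |

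The value 0.43 is the no-difference reference; it is below 0.5 because ties are possible.

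**Step 4. Range.** Take s from 5% to 10% and q from 5% to 30%.

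- f = 0: the gap runs from 0.90 × 0.05 = 4.5 points to 0.95 × 0.30 = 28.5 points.
- f = 0.5: half of that, 2.25 to 14.25 points.
- f = 1: zero throughout.

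The value of f matters as much as the rates, and the choice between the two definitions largely determines it.

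**The case against.** A reader might infer that the comparison is tilted against every-other-day dosing under either definition. The documents do not support that. Three of the five places count alternative oral iron in both arms, and if all of the daily arm's oral need is met that way the gap is zero.

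A reader might also infer that with equally effective regimens the every-other-day arm is bound to show more escalation. That does not follow even from 7.2. A daily-arm patient with the same need may go to IV iron, which counts under both definitions, so different next steps need not give different totals. The 19% vs 10% example assumes that none of the daily arm's oral need is counted.

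Nor is the switch strictly impossible in the daily arm. The 7.2 wording names no arm, and a patient who stepped down under 5.3.4 and then returned to daily would fit it literally. That would be a return to the assigned schedule, not an increase above it, and the protocol does not address it.

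Finally, item 16 is one of 17 secondary outcomes in a feasibility pilot, no test of it is planned, and 8.1 bases the definitive trial on hemoglobin increment.

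These points limit the size and certainty of the effect. What stands is that 7.2 and the week 12 checklist, followed as written, do not count oral changes in the daily arm, and that the broad wording does not say whether more of the same product counts there.

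**Conclusion.** The concern holds in limited form. Under 7.2 and 5.4.2.4 ascertainment of oral escalation is unequal by arm; this follows from the wording and needs no assumed rate. With equal need it can inflate escalation in the every-other-day arm. In the example the gap is 9 points, about 2.3 patients of 26 (26 × 0.09), falling to 4.5 points or zero as half or all of the daily arm's oral need is counted. All these rates are assumptions. Under 3.4, 5.4.2.2 and 10.0 the effect is smaller and may be absent.

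The consequence is for descriptive by-arm estimates and what the definitive trial takes from them, not for a planned test.

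It may be tempting to conclude that the every-other-day to daily switch should be left out of the comparison. That is not supported either. The switch is an increase above the assigned schedule, and escalation ends follow-up, so later IV iron or transfusion in those patients may go unrecorded. Dropping it could favor every-other-day dosing.

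**What to change.** Reconcile 3.4, 5.4.2.2, 5.4.2.4, 7.2 and 10.0 into one outcome definition of escalation. Its oral component should read the same for both arms: any increase above the assigned oral schedule, or a change to another oral iron product. Keep the every-other-day to daily switch inside that component. State that a return to the assigned schedule after a step-down is not an increase above it.

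Report each component by arm. Show the composite twice: in full, and for IV iron, transfusion and anemia-related emergency visit alone.

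The cost is one added line on the week 12 escalation checklist, which now has no entry for alternative oral iron or a daily-arm increase, and one extra table. Medication history is already taken at weeks 4, 8 and 12 and can support the new line. This concerns how events are counted; no clinical escalation rule is proposed.

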8.0 STATISTICAL CONSIDERATION

8.1 Sample Size and Sample Size Justification

The required sample size for this pilot RCT is calculated based on the primary outcome of the definitive study which is the mean hemoglobin increment in each group. For the every other day oral iron group to be considered non-inferior, the mean hemoglobin increment in the every other day oral iron group should not be more than 5 g/L less than the mean hemoglobin increment in the daily oral iron group. This is based on the Cochrane review³¹ of intermittent compared with daily dosing showing that the mean hemoglobin difference between intermittent and daily oral iron was -0.15 g/L (95% CI -2.2 g to 1.9 g). Looking at individual studies within the Cochrane review, the standard deviations for the baseline and end of intervention hemoglobin measurements were approximately 10 g/L. Stoffel et al³⁴ specifically studied the use of ferrous sulfate 300mg po daily over 14 days vs alternate day oral iron over 28 days. The baseline mean hemoglobin in each group was 128 g/L (-SD 117; + SD 140) and 132 g/L (-SD 125; +SD 140) respectively. At the end of the intervention, the hemoglobin was 132 g/L (-SD 125; +SD 140) and 136 g/L (-SD 129; +SD 144), respectively. Thus, the standard deviation for these 2 studies is closer to 10 g/L.

Table 2 below shows the sample size required to confirm non-inferiority of every other day oral iron compared with daily iron based on the true mean difference of the mean increment between the two groups, the standard deviation, the non-inferiority margin and the power of the study. The table also takes into account the adjusted sample size with a 30 % drop out considered.

Table 2: Sample size calculation

True difference of mean increment between two study groups, (g/L) ^{A, D}	Standard Deviation (SD) of the increment (g/L) ^B	Non-inferiority margin for the difference (g/L) ^C	Power	Total Sample size required to confirm non-inferiority	Adjusted sample size with 30% drop out considered ^E
0	5	>-5	80%	28	40
	7.5	>-5	80%	58	84
	10	>-5	80%	102	146

0	5	>-5	90%	36	52
	7.5	>-5	90%	80	116
	10	>-5	90%	140	200
-0.15	5	>-5	80%	28	40
	7.5	>-5	80%	62	90
	10	>-5	80%	108	156
-0.15	5	>-5	90%	38	56
	7.5	>-5	90%	84	120
	10	>-5	90%	148	212

- A. Increment will be calculated from each subject first, and then mean increment for each study group. A difference in the mean increment will be calculated as mean increment in the every other day oral iron group minus mean increment in the daily oral iron group.
- B. Standard deviation (SD) was not available for the increment. It could be estimated from SDs of the pre- and post- treatment hemoglobin level and assumed correlation between pre- and post-hemoglobin. If SDs for the pre- and post- hemoglobin are equal to 10, and correlation between them is 0.5, the estimated SD for the increment is 10. If the correlation between pre- and post- is 0.75, then the estimated SD for the increment is 7.1.
- C. One sided 95% confidence interval of the difference between two groups in the hemoglobin increment will be calculated (every other day minus daily). If the bound of the confidence interval is greater than -5, then non-inferiority can be confirmed.
- D. If we assume the true difference between two groups is -0.15 as reported from the meta-analysis, the sample size required could be slightly larger.
- E. Total sample size was divided by 70% to account for a 30% drop out.

Given that this pilot trial is a proof-of concept study, a sample size of 52 patients was deemed appropriate. Therefore, we will aim to enroll 52 patients to determine the feasibility of the trial and to provide more accurate estimates of the numbers required for a definitive trial. The trial will be deemed feasible if we are able to enroll 52 patients over 2 years at two sites.

The trial will proceed until there are 52 enrolled patients and at least 36 patients who complete the trial to 13 weeks.

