5.0 STUDY METHODS

5.1 Study Design

This is a pilot pragmatic, non-inferiority, open label randomized controlled trial (RCT) in outpatients with iron deficiency anemia to evaluate the effectiveness of oral ferrous sulfate 300mg (60mg elemental iron) once daily versus every other day to improve hemoglobin at 12 weeks post-initiation. Patients will be randomized according to a computer-generated allocation sequence to receive either once daily dosing or every other day dosing. Randomization will be stratified by centre and baseline hemoglobin (hemoglobin \geq 100 g/L OR $<$ 100 g/L). Following randomization, patients will receive oral iron tablets for a period of 12 weeks, with clinical and subjective data collection occurring 1, 4, 8 and 12 weeks following the commencement of oral iron. The study will aim to recruit 52 patients in total, randomizing 26 patients to each study arm. This sample size includes an anticipated 30% drop out rate (see section 8.1).

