5.3.2 Randomization and stratification

Randomization allocation will be performed by Clinical Trial Services at Sunnybrook Health Sciences Centre using a computer generated allocation sequence. The randomization code will be generated in random blocks of 4 to 6, stratified by centre, and hemoglobin at time of randomization (hemoglobin greater or equal to 100 g/L or less than 100 g/L). Randomization will be provided to the sites in opaque numbered envelopes. The study is an open-label study. The research coordinator/assistant will enroll participants for this study.

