8.2 Final Analysis Plan

The results of this pilot trial will be used to assess the feasibility and inform the design of the definitive trial. We will present point estimates of feasibility events, including enrolment, adherence to protocol and accrual, as proportions with 95% confidence intervals. We will present continuous data as means and standard deviations, or medians and inter-quartile ranges, as appropriate.

An intention-to-treat analysis will be performed on all patients randomized for the secondary efficacy outcome. A per protocol analysis will be conducted for patients who have taken at least 90% of the

prescribed doses. Subgroup analysis will be performed on the stratified groups with hemoglobin 100g/L or greater and hemoglobin less than 100g/L. Additional subgroup analyses will include: patients with ongoing bleeding (WHO grade 2 or higher) vs no bleeding; and normal vs. increased CRP (based on the normal range).

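### Cheap improvement: the only between-arm hemoglobin comparison written down is an unadjusted difference in mean increments; an ANCOVA on baseline hemoglobin and centre would usually be more precise

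*Combined protocol and SAP*

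**What the plan says.** Section 8.1 states that the sample size is "calculated based on the primary outcome of the definitive study which is the mean hemoglobin increment in each group". Two notes to Table 2 then define the comparison. Note A: "A difference in the mean increment will be calculated as mean increment in the every other day oral iron group minus mean increment" (the subtracted term being that of the daily arm). Note C: "One sided 95% confidence interval of the difference between two groups in the hemoglobin increment will be calculated (every other day minus daily"), with non-inferiority concluded if the bound lies above -5 g/L. Section 7.2 item 9 defines the increment as the follow-up value minus the baseline value.

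Section 8.2 is the pilot's analysis plan. For continuous outcomes it says: "We will present continuous data as means and standard deviations, or medians and inter-quartile ranges, as appropriate". It adds an intention-to-treat set, a per-protocol set and subgroups. Baseline hemoglobin appears there only as a subgroup split at 100 g/L, and centre does not appear.

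Both variables are used in the design. Section 5.1: "Randomization will be stratified by centre and baseline hemoglobin". Section 5.3.2: "The randomization code will be generated in random blocks of 4 to 6, stratified by centre, and hemoglobin at time of randomization".

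The primary outcome (Section 3.3) is the time to enroll 52 patients. Hemoglobin increment is a secondary clinical outcome.

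**The concern.** A change score uses baseline hemoglobin with its slope fixed at 1. ANCOVA estimates the slope. If the true slope is clearly below 1, subtracting the whole baseline value adds noise, and the interval is wider than it need be against a 5 g/L margin. In Note B's hypothetical, where pre and post SDs are equal, the slope equals the correlation: 0.5 or 0.75.

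The stated interval also takes no credit for the stratified allocation. An analysis that leaves out the stratification factors tends to overstate its own standard error.

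Two things are at stake: the precision of the pilot's one efficacy contrast, and whether the pilot reports the residual SD that a definitive trial with an adjusted analysis would be sized on.

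**Working it through.** **Inputs.** One-sided 5%, margin 5 g/L, true difference 0 (Table 2 and Note C). Pre and post SDs of 10 g/L: "the standard deviations for the baseline and end of intervention hemoglobin measurements were approximately 10 g/L". Correlation *r* from Note B: "If SDs for the pre- and post- hemoglobin are equal to 10, and correlation between them is 0.5", the increment SD is 10; at 0.75 it is 7.1. There are 36 completers, 18 per arm (Section 8.1).

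**The plan's own figures.** Increment SD = 10·√(2(1−r)) gives 10 at r = 0.5, 7.07 at r = 0.75 and 5 at r = 0.875. A noncentral t calculation with N−2 degrees of freedom reproduces the true-difference-0 totals in Table 2 exactly: 28, 58 and 102 at 80% power, and 36, 80 and 140 at 90%. Table 2 is therefore consistent with an unadjusted comparison, and the SD 5 row behind 52 implies r = 0.875 if both SDs are 10.

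**Closed-form comparison at N = 36.**

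- Change score half-width: t(0.95, 34)·SD·√(2/18).
- ANCOVA half-width (baseline covariate): t(0.95, 33)·10·√(1−r²)·√(2/18)·√(1+1/32). The last factor charges for estimating the slope.

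| r | Increment SD | Residual SD | Half-width, change score | Half-width, ANCOVA |
|---|---|---|---|---|
| 0.5 | 10.00 | 8.66 | 5.64 | 4.96 |
| 0.75 | 7.07 | 6.61 | 3.99 | 3.79 |
| 0.875 | 5.00 | 4.84 | 2.82 | 2.77 |

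**Simulation under the planned allocation.** Assumptions: two centres, hemoglobin strata, blocks of 4 or 6, 20% or 50% of patients below 100 g/L, no true centre effect, and 36 complete cases. The ANCOVA contains arm, baseline and centre.

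| r | Mean half-width, change score to ANCOVA (g/L) | Power |
|---|---|---|
| 0.5 | about 5.6 to 4.9 | about 43% to 51% |
| 0.75 | about 3.96 to 3.74 | about 66% to 71% |
| 0.875 | about 2.81 to 2.75 | about 90% to 91% |

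Stratified blocks already limit chance imbalance in baseline. At r = 0.5 the true sampling variance therefore falls by roughly 10–16%, not by the 25% that the ratio (1+r)/2 = 0.75 suggests. The unadjusted interval is slightly conservative there, with coverage of about 96%.

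**When the slope is near 1.** Slope = r × post SD / pre SD. With pre SD 10, post SD 12 and r = 0.75, the slope is 0.9. The increment SD is √(100 + 144 − 180) = 8.0 and the residual SD is 12·√(1 − 0.5625) = 7.94. The closed-form half-width goes from 4.51 to 4.55. Simulated values go from 4.47–4.50 to 4.48–4.58, at most about 2% wider (4.58/4.50 = 1.018).

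**What the documents say about the slope.** They do not give it. The ranges printed in Section 8.1 for the alternate-day study imply SDs of (140−117)/2 = 11.5 before and (140−125)/2 = 7.5 after in one arm, and 7.5 both times in the other. Those women were not anemic (Section 2.1.5). In this trial eligibility caps baseline hemoglobin (Section 5.2.1) and nothing caps week 12, so a larger week 12 SD, and a slope nearer 1, is plausible.

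**The case against.** The strongest objection is that the criticised text is not the pilot's analysis plan. Notes A to C explain a sample-size table for a later study. Section 8.2 is largely descriptive, and feasibility is decided on enrolment alone (Sections 7.1 and 8.1). This stands and limits the weight of the point. It does not remove it: 8.2 promises an intention-to-treat efficacy analysis without an estimator, and the only one written anywhere is unadjusted.

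Second, at the planning row that matches 52 the gain is immaterial, and with a slope near 1 it can turn into a small loss. This also stands. The change is cheap, not free.

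Three stronger readings are tempting and are not supported.

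- A reader might infer that the increment analysis is biased or invalid. It is not. Under randomisation the change score is unbiased, and its interval is at worst slightly conservative.
- A reader might infer that ANCOVA would cut the definitive trial at r = 0.5 from 102 to 78 patients (80% power) and from 140 to 106 (90%), savings of 24 and 34. The unadjusted totals assume unstratified allocation. If the definitive trial is stratified in the same way (an assumption), the unadjusted analysis reaches 80% and 90% power near 98 and 130 patients, so the saving is about 20 and 24–26.
- A reader might infer that the pilot cannot inform an adjusted design unless this is changed. It can: *r* can be recovered from the baseline, week 12 and increment SDs if these are reported on the same patients.

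**Conclusion.** The point holds as an optional refinement. The stated comparison is unadjusted, 8.2 names no alternative, and the two variables that would improve it are already collected and used to stratify. At 36 completers with equal SDs of 10 g/L, the half-width falls by about 12% at r = 0.5 and about 5–6% at r = 0.75, with nothing material at r = 0.875.

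At r = 0.5 the unadjusted mean half-width exceeds the 5 g/L margin and the adjusted one falls just inside it. That is the clearest practical difference.

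These sizes rest on Note B's hypothetical correlations, equal SDs, complete cases and no centre effect. The gain from the centre term cannot be computed because no centre variance is given. The true slope is unknown, so the gain is probable rather than assured. Validity, the feasibility decision and Table 2's arithmetic are not in question.

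**What to change.** In Section 8.2, state that the week 12 between-arm hemoglobin difference and its one-sided 95% confidence interval come from an ANCOVA of week 12 hemoglobin on arm, continuous baseline hemoglobin and centre. Continuous baseline largely captures the hemoglobin stratum, so no separate stratum term is needed. Keep the raw increments by arm as description.

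Report the baseline/week 12 correlation with its confidence interval, and the residual SD, for sizing the definitive trial. The correlation will be imprecise: at n = 36 and r = 0.5, Fisher's z gives about 0.21 to 0.71. Any projected saving for the definitive trial should say whether stratified allocation is assumed.

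The cost is plan wording, two degrees of freedom, and a possible slight loss of precision if the slope is near 1. No new data are needed. The ANCOVA does not deal with week 12 values missing because patients stop assessments after escalation of therapy (Sections 5.4.2.2 and 10.0); that needs its own provision.

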3.3 Primary Outcome Measure

Feasibility: Time to enroll 52 patients

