4.0 HYPOTHESES

We hypothesize that 52 patients will complete the trial within a 2-year period. This includes an expected drop out rate of 30% leaving 36 patients for analysis.

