7.0 CRITERIA FOR OUTCOME ASSESSMENT

7.1 Primary outcome assessment

Feasibility: Enrollment in the trial will be defined as documentation of informed consent for patients approached

If the study is unable to enroll 52 patients in a 2 year enrolment period, the study as it is currently designed will not be deemed feasible.

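### The feasibility verdict rests on 52 enrolments alone with no retention term, and the 36-completer rule turns the stated total of 52 into an open-ended minimum

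*Combined protocol and SAP*

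**What the plan says.** The primary outcome in Section 3.3 is "Feasibility: Time to enroll 52 patients". Section 8.1 sets the favourable verdict: "The trial will be deemed feasible if we are able to enroll 52 patients over 2 years at two sites". Section 7.1 sets the unfavourable one: "If the study is unable to enroll 52 patients in a 2 year enrolment period", then "the study as it is currently designed will not be deemed feasible". Section 7.1 also defines the event being counted: "Enrollment in the trial will be defined as documentation of informed consent for patients approached". Section 5.3.1 uses the word differently: there a patient is enrolled only after consent, bloodwork and confirmed eligibility.

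On size, Section 5.1 states: "The study will aim to recruit 52 patients in total, randomizing 26 patients to each study arm". The Protocol Summary also gives 52 as the planned sample size. On dropout, Section 4.0 says of the 52: "This includes an expected drop out rate of 30% leaving 36 patients for analysis". Note E to Table 2 divides every required total by 70%.

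Section 8.1 then ends with a completion rule: "The trial will proceed until there are 52 enrolled patients and at least 36 patients who complete the trial to 13 weeks". It gives no maximum enrolment and no end date.

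Laboratory completion, questionnaire completion, adherence and step-down are secondary feasibility outcomes (Sections 3.4 and 7.2). They carry no thresholds, and Section 8.2 plans to report feasibility proportions with 95% confidence intervals. Section 8.4 allows early stopping if recruitment or retention difficulty would significantly impair evaluation of the endpoints.

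**The concern.** Section 2.2 says a definitive multicentre trial will be planned if this pilot is feasible. The verdict is therefore a go decision, and as written it can be reached on the day the 52nd consent is signed, before that patient has any follow-up. A design that kept half its patients would receive the same verdict as one that kept 90%, although the plan's sample-size reasoning assumes 70%.

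The completion rule adds a second difficulty. The plan presents 52 as a total with 26 per arm, but a rule that also requires 36 completers fixes the number of completers and lets enrolment float upward. A site, ethics board or funder reading 52 and 2 years would not learn from the plan how far either may be exceeded.

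**Working it through.** **Inputs from the plan.** Margin 5 g/L, true difference 0, SD 5 g/L, 90% power (the Table 2 row that gives 52); one-sided 95% confidence bound (note C); 30% dropout (note E); 52 enrolled and at least 36 completers to 13 weeks (Section 8.1); 24 months (Sections 7.1 and 8.1).

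**Reproducing 36 and 52.** Per arm, n = 2 × SD² × (z₀.₉₅ + z₀.₉₀)² / margin² = 2 × 25 × (1.645 + 1.282)² / 25 = 17.1, rounded up to 18, or 36 in total. With the noncentral t distribution, 18 per arm gives power 0.902, so 36 stands. Inflated for dropout, 36 / 0.70 = 51.4, rounded up to 52. Both figures reproduce.

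**Is 52 enough for 36 completers?** Expected completers at 30% dropout are 52 × 0.70 = 36.4. The required 36 (36/52 = 69.2%) is therefore almost exactly the expected number, with little allowance for chance. With X ~ Binomial(52, completion rate), the chance of falling short is P(X ≤ 35).

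**Total enrolment under the completion rule.** The total is the larger of 52 and the negative-binomial number of patients needed to reach 36 completers. Months are the mean total divided by 52/24 = 2.167 per month.

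| Dropout | P(fewer than 36 of 52) | Mean total | 95th percentile | Months at 2.167 per month |
|---|---|---|---|---|
| 30% (plan) | 0.386 | 53.6 | 60 | 24.7 |
| 40% (assumed) | 0.889 | 60.2 | 71 | 27.8 |
| 50% (assumed) | 0.996 | 72.0 | 87 | 33.2 |

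In every row the verdict is feasible, provided the first 52 enrol within 2 years.

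**Possible cut-offs for a retention term.** Probability that the number completing out of 52 falls below the cut:

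| Cut | 30% dropout | 40% dropout | 50% dropout |
|---|---|---|---|
| Fewer than 36 | 0.39 | 0.89 | >0.99 |
| Fewer than 32 | 0.07 | 0.53 | 0.94 |

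**The case against.** A reader might infer that poor retention can never count against the trial. The documents do not support that. Section 8.4 names retention difficulty as a ground for stopping, and the completion measures will be reported with confidence intervals and used to inform the definitive design. A 50% dropout would be visible to anyone reading the results. What remains is that Section 8.4 has no numeric trigger and no tie to the verdict, so a trial that is not stopped is still declared feasible.

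It is also fair to say that Section 8.1 speaks of the trial proceeding and mentions neither replacement nor recruitment past 52. Over-enrolment is an inference, but no other action can satisfy the rule once fewer than 36 of the first 52 complete. The summary of changes explains the sentence as specifying the number of patients needed for the trial to be considered complete, which fits that reading.

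At the plan's own dropout the excess is small: 1.6 patients on average. The 39% is what any division by 0.70 produces when the target sits at the expected value, so it does not show that 52 was miscalculated. The figures of 60 and 72 rest on dropout rates the plan does not project.

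A reader might also infer that stopping on completers distorts the retention estimate. Under this rule the bias is only +0.2 to +0.7 percentage points at 30% to 50% dropout, so it is no reason for change.

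Finally, a single enrolment criterion is a legitimate choice for a pilot. The objection here is narrower: this plan's own hypothesis and sample-size table depend on retention, and its verdict does not.

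**Conclusion.** The concern holds in this form. The verdict has no retention term, the only retention safeguard is unquantified and separate from the verdict, and the stated total of 52 acts as a minimum with no ceiling.

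The size depends on retention. If dropout is 30% as planned, 52 is exceeded with probability 39%, usually by a few patients. If dropout were 40% or 50%, mean enrolment would be about 60 or 72 and recruitment would pass the 2-year window, with the verdict unchanged.

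The calculation treats completions as independent and assumes steady accrual of 52 per 24 months. The 40% and 50% rates are illustrative. For context, Section 5.3.4 anticipates that about 30% may not tolerate oral iron, and Section 2.1.6 cites up to 40% non-adherence; neither is a dropout rate. The calculation ignores the 13-week delay before completion is known, so actual over-enrolment could be larger. If patients who leave assessments after escalation of therapy (Sections 5.4.2.2 and 10.0) count as non-completers, completion would be lower still.

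**What to change.** 1. Count the 52 as randomized patients rather than consents, and bring Section 7.1 into line with Section 5.3.1.
2. Choose one meaning for 52. Either restate it as a minimum with a maximum enrolment and an end date, or fix the number at 52 and drop the 36-completer condition. A maximum of 60, for example, is the 95th percentile at 30% dropout; P(at least 36 of 60 complete) is then 0.96 at 30% dropout and 0.56 at 40%.
3. Add a retention term to the verdict, based on completion to 13 weeks among the first 52 randomized. 'Feasible' requires 52 randomized within 24 months. If fewer than 36 of those 52 complete, the verdict becomes 'feasible with changes', not 'infeasible', and the completion proportion with its 95% confidence interval sets the dropout inflation for the definitive trial.
4. Reconcile the Protocol Summary with Sections 4.0, 5.1, 7.1, 8.1 and 8.4. Section 4.0 also hypothesises that 52 will complete, against 36 left for analysis.

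The cost is protocol wording, a verdict that waits for the 52nd patient's follow-up, and, if the number is fixed at 52, possibly fewer than 36 completers. With the cut at 36, the 'with changes' label would apply about 39% of the time even when dropout is exactly 30%. If that is too often, a cut at fewer than 32 of 52 would apply about 7% of the time at 30% dropout, 53% at 40% and 94% at 50%. The sponsor should choose the cut in advance with these rates in view.
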